Access to the KCL site is highly restricted: key-locked cabinets are stored in key-locked offices, the doors to which are locked when research team members are not present. Access to office buildings and corridors is restricted to identity card holders by means of swipe card readers. Although the exact security arrangements of participating NGOs may vary between sites, access is also highly restricted due to the need to protect trafficked people from potential risk of harm and staff offices are locked when staff are not present.

Hard copy data may be transferred between the NGO and the university manually or using a signed for and tracked mail service. Manual transfers are scheduled for when the study PI or manager is visiting the site. The data should be signed out by the PI/post-doctoral researcher and counter-signed by a representative of the NGO. The data should be transferred into a padlocked bag and taken directly to the university site, where they must be signed in and securely stored.

If data are removed from the filing cabinet by a member of the research team (e.g. for data entry into the MACRO database) they must be signed out and signed back in upon return. Data must be returned to the filing cabinet if the researcher is leaving the office even if temporarily.

The departmental postal address for the location within the College at which research data will be stored during and after the study is as follows: [name].

Research data entered into the electronic MACRO database will be stored on the secure university network/server.

Project data (i.e. data routinely collected by the NGO) will be extracted by The Salvation Army for participants who have provided their consent. Extracts will be securely transferred from The Salvation Army to the research team using the KCL Secure File Transfer service and

downloaded to the secure internal university network/server. Data contained within the extract will be entered into the MACRO database and checked before deletion.

Audio recordings of the qualitative interviews will be taken on encrypted digital recorders. Recordings will be transferred onto the secure internal university network with password-protected permissions. Audio files will then be removed from the recording device. Audio files will then be securely transferred to a professional transcription agency following signature of a confidentiality agreement. Transcripts will be downloaded to the secure internal university network and checked against the audio file: after checking, the audio file will be deleted from the university network/server. Transcripts will be anonymised during this checking process.

As per funder guidance, research data will be stored for 10 years after project completion.

19c Data access

Access to participants' personal data will be restricted to the study team (including NGO researchers, for the purposes of data collection and transfer, and Clinical Trials Unit staff), interpreters, transcribers, and auditors. The only exception to that is if a participant discloses something that leads the research team to believe that the participant or another person is at serious risk of harm. In this scenario, the researcher will explain to the participant that they need to break confidentiality to respond to the identified risk. This is detailed on the participant information sheet.

A confidentiality agreement will be in place with transcribers and interpreters.

20. Statistical methods

20a Statistical methods for analysing primary and secondary outcomes

To assess whether receipt of advocacy support is associated with improved mental health a paired samples t-test (or nonparametric equivalent) to assess mean change over the study period (6 months) will be conducted.

20b Methods for additional analyses

To assess whether change over times varies with intervention characteristics (amount of advocacy support received by study participant RQ2 or NGO service characteristics) change scores will be constructed over the intervention period.

The "dose of the support received" will be quantified (e.g. duration in terms of session length, frequency, and the period over which sessions are received; structural and service characteristics NGOs) and change scores will be regressed on this dose. Possible confounders of the dose-response relationship will be identified by testing whether any baseline participant characteristics (e.g. gender, immigration status) predict change over time. Any such potential confounders will then be adjusted for in a second step which regresses the change changes on the dose variable and the putative confounders.

These analyses (which do not include a control group) are based on the assumption that a control group would not exhibit any change over the intervention period. In order to assess the

impact of departures from this assumption on the evaluation of the advocacy support intervention sensitivity analyses will be conducted. Literature evidence will be used to generate a possible distribution of mean outcome change in a hypothetical control group of eligible trafficked woman waiting to start the support program (37); and will then include such sensitivity parameters in our analyses models to study their impact on the estimation of the prepost effect.

20c Methods for handling missing data

In the case of missing data in the CORE-OM outcomes, putative baseline confounders, or process variables, multiple imputation (MI) will be used to ensure that the analyses remain valid under an appropriate missing at random assumption. This will enable us to (multiply) impute realistic outcome patterns including allowing for process variables such as discontinuation of advocacy support to drive loss-to follow-up.

21. Economic evaluation

An exploratory analysis of service use, costs and effects before and after intervention will be undertaken with the results presented using a cost consequences framework, which is recommended for the evaluation of complex interventions that have multiple effects (38). This work will be used to support the generation of recommendations for future research and the development and testing of economic measures appropriate for this population. Specific objectives will include the following:

- 1. Calculate the cost of the advocacy interventions taking a micro-costing (bottom-up) approach (38).
- 2. Develop and test an appropriately adapted version of the AD-SUS to collect data on the use of all health and social care services (taking the NHS/personal social services perspective preferred by NICE) and use this data to estimate the cost per participant through the application of nationally applicable unit costs (39).
- 3. Assess whether receipt of advocacy support is associated with changes in service use and costs (i.e. before and after intervention).
- 4. Test the acceptability and relevance of preference-based measures of health-related
- 5. quality of life (HRQoL) for the current population, including the EQ-5D-5L (EuroQol 5 dimensions, 5 levels), the SF-6D (Short Form 6 dimensions), and the ReQoL-10, which are all capable of generating quality adjusted life years (QALYs) suitable for future economic evaluations (25, 27, 40).
- 6. In line with the proposed clinical analyses noted above, explore whether receipt of advocacy support is associated with improvements in HRQoL and QALYs and whether change over time varies with participant characteristics at baseline or with the structural or service characteristics of NGOs.

22. Qualitative analysis

Analysis of qualitative data collected in study 2 will support the testing of initial programme theory using empirical data and the refinement of programme theory. This will involve moving iteratively between case analysis, refinement of programme theory, and further data collection to test emerging theory about how advocacy interventions improve outcomes, for whom, and under what circumstances. The coding of qualitative data will be inductive, deductive, and

retroductive (i.e. informed by theory, emerging from the data, and making inferences about mechanisms based on interpretations of the data).

In the first stage of analysis, we will develop a detailed narrative for each of the three study sites. We will combine data on intervention receipt from study 1, and qualitative data from study 2 to describe service model and structures, staffing, and intervention provision (including session frequency, duration, and type). In the second stage, and to test proposed context mechanism outcome (CMO) configurations in relation to intervention components, we will conduct within-case analyses to look for evidence threads that suggest different ways in which the proposed mechanisms operated in practice and associated the contexts and outcomes, while seeking to identify alternative mechanisms and explanations. We will then seek to identify and understand interactions between specific mechanisms, the contexts in which they were triggered, and the associated outcomes. These analyses will also investigate whether the activation of mechanisms from one component depends on the outcomes of another component. In the final stage of analysis, we will conduct cross-case comparisons and synthesis, comparing CMO models emerging from the sites, and refining programme theory. This analysis will identify contextual factors that are common across all sites and re-examine the associated mechanisms and outcomes, which will produce evidence on the ways in which advocacy interventions influence the mental health and wellbeing of trafficked people.

Findings from this study – an understanding of what works for whom and under what circumstances and refined programme theory - will be used to provide practical guidance on orienting services into configurations that seem to improve the mental health and wellbeing of survivors of trafficking.

23. Monitoring

A DMEC is not required.

24. Harms

Collection of information regarding adverse events is limited to death. In the event of participant death, a Withdrawal Form must be completed by the Study Manager and information sought from the recruiting NGO regarding date and cause of death.

With regards to harms that may arise during interviews, we will follow the WHO Ethical and Safety Guidelines on Interviewing Trafficked Women (47) and standard operating procedures adapted from our previous research with trafficked people that set out measures to be taken to minimise risk to researchers, distress and risk to participants, and steps to be taken if risks of serious harm to the participant or others are identified.

25. Auditing

The PI has overall responsibility for the study and will allow audit by providing the study sponsor direct access to source data and other documents as required.

26. Research ethics approval

The study gained approval from the King's College London (KCL) Research Ethics Committee (HR-19/20-14424) and from the Salvation Army Research Ethics Committee and will be

conducted in full compliance with the current version of the Declaration of Helsinki, relevant regulations, and MRC Good Clinical Practice (GCP) guidelines.

All researchers involved in data collection will undertake and/or update GCP training on obtaining informed consent when conducting research plus training on obtaining informed consent when conducting research with vulnerable populations.

27. Consent

The General Medical Council (GMC) guidance on obtaining consent from adults and young people for research purposes will be followed (41). Prior to the recruitment process, NGO and KCL researchers will undertake Good Clinical Practice (GCP) training on obtaining informed consent when conducting research, supplemented by training on obtaining informed consent when conducting research with vulnerable populations.

During the recruitment stage, potential study participants will be offered clear information in their own language, verbally and in writing (i.e. Participant Information Sheet), about the purpose, subject and nature of the study and what would be required of them if they consented to participate. Professionally translated copies of the Participant Information Sheet (PIS) and Consent Form will be provided to NGOs. Information on potential benefits and risks of participating will be detailed in the Participant Information Sheet (PIS). The PIS will additionally set out why they have been asked to participate in the study, what participation will involve, that participation is voluntary and will not affect the service they receive, and that consent to participate can be withdrawn at any time without having to provide a reason. In describing what participation involves, the PIS will state that all participants will be asked complete questionnaires at three time points.

Potential participants will be given a minimum of 24 hours to consider their participation in the study before consent is sought, and it will be emphasised that participation is voluntary. During the formal consent process, each participant will be informed that their responses will be anonymous and confidential (e.g., no names would be used on questionnaires, and questionnaires will not be seen by anyone outside the study), and that the study is not related to any immigration or policing procedures. Participants will be advised that they do not have to answer any questions, if they do not wish to, that they may take a break or terminate the interview at any time, and that declining to participate will not in any way affect the services they are receiving. Participants who decline to participate in the study will be asked if their basic socio-demographic characteristics (gender, age, and country of origin) can be collected anonymously to determine whether there are differences between participants and non-participants.

Only people who meet all inclusion criteria and no exclusion criteria and can provide informed consent will be recruited. Individuals who are interested to participate will be asked by NGO researchers to provide written consent. Prior to the administration of questionnaires, participants will be reminded that participation is voluntary and will not affect the service they receive, that they do not have to answer questions if they do not wish to, and that they can take a break or terminate the questionnaire at any time. Questionnaires will be administered only by trained individuals and in private.

28. Confidentiality and anonymity

The information provided by participants will be confidential and pseudo-anonymised. In some situations, however, it may be necessary to disclose personal information without a patient's consent if it is in the public interest (i.e. where a failure to do so may expose the patient or others at risk of death or serious harm). The limits of confidentiality are explained on the participant information sheet and will be discussed with all participants as part of the informed consent process.

All participants will be assigned a unique PIN. PINs will be used at all times when managing the research data. Any data collected that includes identifiable details about study participants will be stored separately from the research data. To reduce the risk of attribute disclosure, cell counts less than or equal to 5 will be suppressed.

29. Declaration of interests

The Principal Investigator declares no conflict of interest.

30. Dissemination policy

The protocol will be submitted for publication on an open access basis. The study results will be submitted for publication on an open access basis. A lay summary of the study findings will be produced and disseminated to study participants who indicated on their consent forms that they wished to receive a copy of study findings. Briefing notes will summarise study findings for recruiting organisations and policymakers.

ICMJE authorship guidelines will be followed.

Public access to the participant-level dataset is not planned.

References

- UN General Assembly. Protocol to Prevent, Suppress and Punish Trafficking in Persons, Especially Women and Children, Supplementing the United Nations Convention against Transnational Organized Crime. 2000 [Available from:
- https://www.refworld.org/docid/4720706c0.html.
- 2. Walk Free Foundation. Global Slavery Index. Australia: Walk Free Foundation; 2018.
- 5. Helen Bamber Foundation. Addressing mental health needs in survivors of modern slavery: a critical review and research agenda. London; 2016.

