Failure to provide effective mental health support for trafficked people increases the risk of persisting mental ill health and, in consequence, poor social outcomes, which carry costs for both individuals and society. Yet, evidence on what helps people's recovery is absent (5, 6). A systematic review of published and unpublished experimental, quasi-experimental, and pre-experimental studies reporting on the effectiveness of post-exit intervention programs for trafficked people identified only six eligible studies (7). The majority of these studies were appraised as having been poorly designed and executed, none had a sample size larger than 55 and the review failed to reach any conclusions with regards to what constitutes an effective intervention for this population.

In the UK, survivors of human trafficking are entitled to government-funded support that aims to help them recover from abuse and rebuild their lives. Data show a year on year increase in the number of trafficked people being referred into support, with 1,856 people referred for support in 2017/18, 1,554 in 2016/17, 1,400 in 2015/16, and 1,097 in 2014/15 (8). Support is currently provided by a network of 12 non-governmental organisation (NGOs) that provide specialist post-trafficking support as part of a Victim Care Contract (VCC) managed by The Salvation Army. The provision of this support represents a significant financial commitment from the government at an average of £18m per year (9).

VCC support follows an "advocacy" model, although the specific service model and the intensity of support varies between organisations (10, 11). Advocacy interventions are defined as strengths-based, survivor-centred services based on empowerment models, in which caseworkers help service users to make sense of their situations, achieve self-identified goals, link them to community services, and provide ongoing support and informal counselling (12). Caseworkers generally do not have a background or training in psychological therapies and do not provide counselling or other specified forms of therapy.

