Two small (n=28 and n=36) uncontrolled studies examined the impact of advocacy interventions with refugees in the USA. These studies found participants reported reduced psychological distress following intervention (13, 14). One controlled study found reduced depression scores in both intervention and control groups, but reported likely contamination in their control group, with informal support having been provided to controls during data collection (15). A Cochrane review of 13 randomised controlled trials of advocacy interventions for victims of domestic violence concluded that intensive advocacy improved everyday life and reduced experiences of physical violence (12).

The generalisability of these findings to trafficked people is not clear. However, findings that risk of mental disorder is higher for survivors of human trafficking who have increased social needs and lower levels of social support (3, 4, 16) suggests a need for interventions that that address current stressors and improve social support. The evaluation of advocacy-based interventions is therefore a priority need in informing the design of future services and to guide commissioning and investment. However, outcomes have not been evaluated (either in the UK

or elsewhere): the effectiveness of advocacy interventions in reducing psychological distress among survivors of trafficking remains unknown.

7. Aims & objectives

The current study aims to assess the effectiveness of advocacy-based casework support in improving the mental health of trafficked people. We hypothesize that advocacy-based casework support for trafficked people is beneficial and dose-dependent. There are no data examining how service level variations or specific components of care affect mental health outcomes for trafficked people. We therefore additionally propose research to explore which service configurations and components of support appear most beneficial for which trafficked people. This research will be among the first rigorous intervention evaluation studies to assess the effectiveness of a post-trafficking intervention and will contribute to public mental health initiatives by providing evidence for a understudied group at high risk of mental health problems (17).

Specific objectives of this study are to:

- 1. Evaluate the effectiveness of advocacy interventions in improving the mental health of people who have been referred into NGO services for post-trafficking support through the UK NRM.

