- 2. Evaluate whether aspects of the advocacy intervention experience thought to improve outcomes modify the effect of the advocacy intervention on mental health and wellbeing; in particular, to test whether
 - a. the effect changes as the amount of support received increases
 - b. the effect varies according to structural or service characteristics of NGOs;
- 3. Assess the service use and costs associated with advocacy interventions for trafficked people who have been referred into NGO services

8. (a) Study design

Exploratory prospective uncontrolled cohort study and realist evaluation with assessments at baseline (T1) (i.e. at or soon after onset of advocacy support), at 3 months follow up (T2) and at 6-months follow-up (T3). The primary outcome is reduced psychological distress (measured using the CORE-OM) at 3 months follow up (T2) compared with baseline (T1).

(b) Rationale for not including a control group

It is not feasible to recruit a control group for the following reasons: (1) All trafficked people who enter the National Referral Mechanism (NRM) are entitled to government-funded NGO support. Support is provided by a national network of NGOs; there is enough capacity, so NGOs do not operate waiting lists that could serve as a source of controls; (2) Trafficked people who enter the NRM but elect not to receive NGO support are extremely difficult to identify for recruitment. The PI's previous research showed that it is not feasible to recruit from settings such as the NHS and Local Authorities (4).

This study will therefore assess whether mental health among survivors of trafficking improve over the period during which advocacy support is provided, with measures taken at or soon after onset of advocacy intervention, at 3 months follow up, and at after a further 6 months follow up. To support the interpretation of any detected change as a causal intervention effect in the absence of a control group dose-response relationships between change over time and

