grounds decision prior to entry into NGO support, though this is not always the case. Individuals who have entered NGO support prior to receiving a reasonable grounds decision who then receive a negative decision are exited from support services.

A second "conclusive grounds" decision regarding an individual's claim to have been trafficked will then be made. The target for decision-making is 45 days, though in practice the decision-making period is often longer. An individual who receives a negative conclusive grounds decision is determined not to be a victim of trafficking, and is exited from support services. Individuals who receive a positive conclusive grounds decision can continue to receive NGO support services; the default support period in England and Wales is 45 days. Individuals can, however, apply to extend their access to support services by up to 6 months (renewable) via the Recovery Needs Assessment process.

Prior to intake, an Initial Assessment will be completed in order to determine eligibility, risk, and urgent needs. Individuals who lack mental capacity, who have severe drug and alcohol problems, or who are acutely mentally unwell are not supported by the NGO services. After arrival at NGO services, a Detailed Needs Based Assessment is undertaken, followed by an Individual Support Plan. The intervention is considered to commence at the initiation of the individual support planning process. The support plan is individualised but organised according to the following categories:

- 1. Secure and appropriate accommodation
- 2. Provision of subsistence payments
- 3. Access to emergency health services
- 4. Advocacy for specialist services
- 5. Assistance with criminal proceedings
- 6. Access to education for dependent school age children
- 7. Access to compensation

These categories align to the entitlements of survivors of trafficking under the Council of Europe Convention on Action Against Trafficking in Human Beings (ECAT) rather than to advocacy activity categories described by the initial programme theory.

Other concomitant care and interventions are permitted during the trial (e.g. psychological interventions); data on receipt of other health and social care services are collected (see section 12, outcomes).

12. Outcomes

Study 1 – Cohort Study

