Outcomes align with the initial programme theory for the advocacy intervention developed in collaboration with NGOs and informed by relevant literature. Commonly-used, well-validated measures have been chosen where these exist for the outcome of interest and items are relevant to the experiences of trafficking survivors.

Primary outcome

The primary outcome is psychological distress at T2 versus T1. Psychological distress will be measured by the Clinical Outcomes in Routine Evaluation- Outcome Measure (CORE-OM), a 34-item questionnaire which measures global psychological distress. The questionnaire was

designed to assess efficacy and effectiveness across multiple disciplines offering psychological therapies (19). It has good internal and test-retest reliability (0.75-0.95), large differences between clinical and non-clinical samples, and good sensitivity to change (19). Validation work in general population samples shows the CORE-ORM is highly correlated (r=0.77) with the Clinical Interview Schedule-Revised (CISR), supporting convergent validity (20). It has good acceptability in domestic violence research (21, 22) and has been used in research with survivors of human trafficking (23).

Secondary outcomes

Secondary outcomes are CORE-OM score at T3, and health-related quality of life, social support, unmet needs, perceived safety and risk of harm, autonomy, and use of health and social care services at T2 and T3.

- 1. **Health-related quality of life** will be measured using the EQ-5D-5L and SF-12 (25, 26) and the Recovering Quality of Life-10 (ReQoL-10) (27), a new 10-item Patient Reported Outcome Measure (PROM) that has been developed to assess the quality of life for users of mental health services.
- 2. Use of health and social care services will be measured using an adapted version of the Adult Service Use Schedule (AD-SUS) (24). The AD-SUS is a structured instrument which collects data on participants' use of health and social care services for the three-months preceding interview (at baseline) or since the previous interview (at any follow-up point).

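### Psychological therapy during follow-up is permitted and recorded, but no stated CORE-OM analysis uses the record, and the listed confounders of the dose-response omit treatment in progress at T1

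*Protocol*

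**What the plan says.** **Aim.** Objective 1 in section 7 is to "Evaluate the effectiveness of advocacy interventions in improving the mental health of people who have been referred into NGO services". Section 8(b) says that dose-response relationships will be assessed to help interpret any change as a causal effect of the intervention.

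**What advocacy is.** The background section states: "Caseworkers generally do not have a background or training in psychological therapies and do not provide counselling or other specified forms of therapy". It also defines advocacy as including links to community services and informal counselling. The support-plan categories in section 11 include advocacy for specialist services.

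**Other care.** Section 11 states: "Other concomitant care and interventions are permitted during the trial (e.g. psychological interventions); data on receipt of other health and social care services are collected". Under section 12 the AD-SUS "collects data on participants' use of health and social care services for the three-months preceding interview (at baseline) or since the previous interview". Section 13 schedules it at T1, T2 and T3. Its stated roles are as a secondary outcome (section 12) and in the economic evaluation (section 21), which will "Assess whether receipt of advocacy support is associated with changes in service use and costs (i.e. before and after intervention".

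**Analysis.**
- 20a gives a paired t-test, or a nonparametric equivalent, on mean change.
- 20b regresses change scores on dose and adjusts for baseline participant characteristics found to predict change. Gender and immigration status are the examples given.
- Section 12 lists eight additional baseline measures as possible confounders: gender, age, nationality, immigration status, housing status, and type, duration and recency of exploitation.
- 20b acknowledges that the analyses assume no change in a control group. It plans a sensitivity analysis built on a "possible distribution of mean outcome change in a hypothetical control group of eligible trafficked woman waiting to start the support program".

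**The concern.** Each participant's comparator is the same person at T1. If therapy starts between T1 and T2, background treatment differs between the two assessments. Section 12 describes the CORE-OM as designed to assess psychological therapies and sensitive to change, so it can be expected to register therapy gains. The protocol collects the data needed to see how far this happens but gives them no part in interpreting the primary outcome.

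The sharper exposure is in the dose-response. Someone already in treatment at T1 may receive more or less advocacy and may also change more or less on the CORE-OM. Treatment at T1 could then confound the analysis that section 8(b) relies on for a causal reading. It precedes the follow-up period, so adjusting for it does not remove anything that advocacy achieves after T1.

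**Working it through.** **1. The protocol's own figures (section 14).** Inputs: 450 recruited, 25% loss by T2, SD 18, two-sided 5% paired t-test, 3.2 points detectable at T2.
- Analysed at T2: 450 × 0.75 = 337.5, taken as 337.
- Standard error: 18/√337 = 0.98 points.
- Noncentral-t power for 3.2 points (3.2/18 = 0.178 SD): 0.902. The stated 90% is reproduced.
- Smallest observed mean change that reaches significance: t(0.975; 336 df) × 0.98 = 1.93 points.

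No sample-size figure is in dispute. The design can declare quite a small mean change significant.

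**2. Where the therapy record is used.**
- Paired comparison (20a): not used.
- Dose-response (20b): only baseline characteristics are eligible. Treatment at T1 is not among the eight listed measures, though the open wording of 20b would allow it.
- Hypothetical-control sensitivity analysis (20b): drawn from literature, with no stated link to recorded therapy.
- Multiple imputation (20c): uses process variables, which section 12 defines as advocacy support data.
- Service-use outcome and costs (sections 12 and 21): used.

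**3. Two kinds of therapy.** Therapy obtained because a caseworker arranged it lies on advocacy's causal path and counts towards its total effect. Therapy that would have been obtained anyway would also occur in a group without advocacy, so it belongs to the control-group change that 20b proposes to vary. What is missing is a way to set the range of that parameter from therapy uptake in this cohort.

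**4. Illustration only.** The protocol gives no uptake *p* and no mean therapy gain *g*. Assume that advocacy adds nothing, that all the therapy would have happened anyway, n = 337 and SD of change 18 before mixing. Mean change is p × g and the SD is √(18² + p(1−p)g²). The gains tried are 5 points (the number that section 14 gives as the reliable change index, an individual-level threshold borrowed here only as a round value) and 9 points (0.5 × 18).

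| Uptake | Mean change, g = 5 | P(significant) | Mean change, g = 9 | P(significant) |
|---|---|---|---|---|
| 10% | 0.5 | 8% | 0.9 | 15% |
| 20% | 1.0 | 17% | 1.8 | 43% |
| 30% | 1.5 | 33% | 2.7 | 76% |
| 40% | 2.0 | 52% | 3.6 | 94% |

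Uptake that alone would produce 3.2 points: 3.2/5 = 64%, or 3.2/9 = 36%.

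**5. What restricting to people without therapy would cost.** At 40% uptake, 337 × 0.60 ≈ 202 remain. The standard error is 18/√202 = 1.27, and power for 3.2 points falls to 0.71.

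**The case against.** The strongest defence is that access to other care is part of what advocacy does. Linking people to services and advocating for specialist care are written into the intervention, and use of services is a secondary outcome aligned with the programme theory. For the total effect of advocacy as NGOs provide it, leaving post-baseline therapy unadjusted is the right default. That stands, and the primary analysis should not be adjusted for therapy received after T1.

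A second defence is that the control group imagined in 20b lacks the support programme, not all other care, so its change already includes therapy that people would have had anyway. In concept that also stands. A reader might infer that therapy is a separate bias, untouched by the sensitivity analysis; the protocol does not support so strong a reading. The gap is that the parameter is not linked to the therapy data.

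Third, the confounder wording in 20b is open, the AD-SUS is itself a baseline instrument, and covariate lists are often completed in the SAP. Treatment at T1 is therefore not excluded. But section 12 does name the candidates and leaves it out.

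Fourth, the study is labelled exploratory, 20a speaks of association, before-and-after service use will be reported, and the survivor interviews ask about changes due to other circumstances. These soften the point. They do not remove the causal aim in section 8(b), and none of them relates therapy to CORE-OM change.

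**Conclusion.** The point holds in a limited form. The protocol permits therapy, records it at every assessment, and uses the record in no stated CORE-OM analysis. Its listed confounders of the dose-response omit treatment in progress at T1.

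The size cannot be determined from the protocol. The 8% to 94% range above depends wholly on the assumed uptake and gain, on a zero advocacy effect, and on none of the therapy being due to advocacy. A reader might take these percentages as false-positive rates of the primary test. They are not: the test's null is zero mean change, and in these scenarios the mean does change. What is uncertain is how to attribute it.

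A reader might also infer that effectiveness should be claimed only if the change persists in people who had no therapy. That does not follow. Such a subset is defined by a post-baseline event and excludes gains that advocacy produced by arranging therapy. At 40% uptake it would have about 71% power for 3.2 points, so a real effect could easily be missed.

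**What to change.** 1. In 20b, add psychological or psychiatric treatment in the three months before T1, taken from the T1 AD-SUS, to the dose-response adjustment set, and name it among the candidate confounders in section 12.
2. In 20a, state that the T1-T2 change is change under advocacy together with other care received. Tabulate the share in therapy at T1 and the share starting it by T2.
3. Add a T1-T2 CORE-OM analysis by therapy receipt, labelled as sensitivity only. Use observed uptake when setting the range of the planned hypothetical-control parameter.

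This costs some wording, one covariate, one table and one additional analysis. It needs no new participants, visits or instruments. The downside lies in item 3: the analysis conditions on a post-baseline event, loses precision and removes benefit that advocacy achieved by arranging therapy. The text should say that it informs interpretation and is not a condition for concluding effectiveness.
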